7.1.1 Adverse Event Definition

An AE is any untoward medical occurrence in a patient or clinical investigation subject administered a pharmaceutical product and may not necessarily have a causal relationship with the administered treatment. An AE can therefore be any unfavorable and unintended sign (including a clinically significant laboratory abnormality), symptom, or disease temporally associated with the use of an investigational product, whether related to the investigational product. Pre-existing conditions, diseases, or disorders are not considered AEs unless there is a change in severity or frequency.

7.1.2 Serious Adverse Events and Serious Unexpected Adverse Events Definition

An SAE is any untoward medical occurrence that meets one of the following:

- Results in death
- Is life-threatening (at the time of the event)
- Requires inpatient hospitalization or prolongation of existing hospitalization

- Results in persistent or significant disability/incapacity
- Is a congenital anomaly/birth defect

A serious and unexpected AE is an SAE that is not identified in nature, intensity, or frequency in the risk information included in the Product Label for the drug.

Important medical events that may not result in death, be life-threatening, or require hospitalization may be considered a serious adverse drug experience when, based upon appropriate medical judgment, they may jeopardize the study subject and may require medical or surgical intervention to prevent one of the outcomes listed in the definition.

7.1.3 Methods/Timing for Assessing, Recording, and Analyzing Safety Endpoints

AEs will be assessed at study visits starting after the first administration of investigational product until the final follow-up visit. However, SAEs will be collected from the time of informed consent onward. General symptoms will be collected via an open-ended question: "How have you been feeling since your last visit or the last time we spoke?"

AEs will be documented in the source records, and recorded on the CRFs using accepted medical terms and/or the diagnoses that accurately characterize the event. When a diagnosis is known, the AE term recorded on the CRF will be the diagnosis rather than a constellation of symptoms. The investigator will assess all AEs for seriousness, relationship to investigational product, and severity. When an event has not resolved by study closure, it will be documented on the AE CRF as "ongoing."

If a female has a positive or borderline pregnancy test after enrollment, the medical monitor will be contacted, and the pregnancy will be recorded as an AE. In accordance with standard clinical practice, results of pregnancy tests will not be disclosed to the subjects' parents unless the subject is age 15 or younger. Parents will be informed of this point during the parent permission process. The site will contact the subject at least monthly and document the subject's status until the pregnancy has been terminated or completed. The outcome of the pregnancy will be reported to the medical monitor, funding agency, and the Brown IRB without delay within 24 hours of knowledge of the event if the outcome is a SAE (e.g., death, abortion, congenital anomaly, or other disabling or life-threatening complication to the mother or newborn).

All AEs, including clinically significant abnormal findings on laboratory evaluations, regardless of severity, will be followed by study physicians until satisfactory resolution (the event either resolved or stabilized and is not expected to resolve in the near term). AEs will be reported up to 2 weeks following completion of, or termination from investigational product administration. At the follow-up telephone contact, AEs will be recorded and followed to resolution only if they are serious, or if the study physician assesses them to be clinically significant.

7.1.4 Classification of Adverse Event Intensity and Relationship to Investigational Product

For each recorded AE or SAE, a study physician must assess severity. For those AEs included in the National Cancer Institute Common Terminology Criteria for Adverse Events (CTCAE version 5.0), these severity criteria will apply. For those not listed in the CTCAE, the following criteria will be used:

Mild: An event that is usually transient, requiring no special treatment, and does

not generally interfere with the subject's daily activities.

Moderate: An event that interferes with usual activities of daily living, causing

discomfort but poses no significant or permanent risk of harm to the subject. The event is usually ameliorated with additional specific

therapeutic intervention.

Severe: An event that interrupts usual activities of daily living or significantly

affects clinical status. The event poses a significant risk of harm to the subject and hospitalization may be required, and typically requires

intensive therapeutic intervention.

Life-threatening An event that puts the subject into imminent risk of death without

intervention.

Clinical chemistry severity and blood pressure increases will be graded in accordance with the CTCAE version 5.0.

The investigator must assess relationship to the investigational product based on the following criteria:

Unrelated: The subject did not receive the investigational product, the temporal sequence

of the AE/SAE onset relative to administration of the investigational product

is not reasonable, or there is another obvious cause of the AE/SAE.

Unlikely: There is evidence of exposure to the investigational product but there is

another more likely cause of the AE/SAE.

Possible: There is evidence of exposure to the investigational product, the temporal

sequence of the AE/SAE onset relative to administration of the investigational product is reasonable, but the AE/SAE could have been due to another equally

likely cause.

Probable: There is evidence of exposure to the investigational product, the temporal

sequence of the AE/SAE onset relative to administration of the investigational

product is reasonable, and the AE/SAE is more likely explained by the

investigational product than by any other cause.

Definite: There is evidence of exposure to the investigational product, the temporal

sequence of the AE/SAE onset relative to administration of the investigational

product is reasonable, the AE/SAE is more likely explained by the

investigational product than by any other cause, and the AE/SAE shows a pattern consistent with previous knowledge of the investigational product or

investigational product class.

7.1.6 Outcomes and Actions Taken

All unresolved AEs will be followed for a minimum of 14 days (unless the AE is an ongoing pregnancy which must be followed to conclusion) after the subject's End of Study visit, unless the investigator's judgment dictates otherwise, the event has resolved or stabilized prior to the 14-day period, or the subject is lost to follow-up.

Atomoxetine – Proof-of-Concept Trial

NCT#: NCT04565288

Investigators are not obligated to actively seek AEs or SAEs in former study subjects that occur following the follow-up period.

For each recorded AE or SAE, the investigator must assess outcome at the time of last observation, as follows:

Fatal: The subject died.

Resolved without Sequelae: The AE or SAE has ended.

Resolved with Sequelae: The AE or SAE has ended but changes are noted from

baseline.

Unresolved – Ongoing: The AE has not ended and is ongoing at the end of the

reporting period (i.e., 14 days after the final Follow-up visit) and the investigator deems that further follow up is not

medically required

Unknown – Lost to Follow-up: Lost to follow-up after repeated unsuccessful attempts to

contact the subject.

Actions taken with respect to investigational agents (discontinuation or not) will also be recorded. In addition, if the AE was treated (medications or other physical measures), this will also be recorded.

7.2 Reporting Serious Adverse Events

7.2.1 24-hour Reporting Requirements (Initial Report)

Any SAE, including death due to any cause, which occurs to any subject from the time of admission through discharge whether related to the investigational product, must be reported *within 24 hours* of knowledge of the event to the medical monitor or alternate.

The following information must be provided with the initial report of an SAE:

- Name of person reporting the SAE/unexpected AE
- Subject's ID number
- Name of the principal investigator and institution
- Date the subject signed informed consent
- Date first dose of investigational product was ingested
- Description of the SAE/unexpected AE
- Date and time of Onset
- Date/time of administration of last dose of investigational product prior to the SAE/unexpected AE
- Severity of the SAE/unexpected AE
- Investigator's assessment of the relationship of the SAE/unexpected AE to investigational product (related, possibly related, probably related, unlikely related, not related)
- Any action taken with the investigational product, alteration to protocol defined schedule, diagnostics, and treatments secondary to the SAE/unexpected AE.

3-Day Supporting Documentation Requirements

Written documentation for all SAEs/unexpected AEs must be received by the medical monitor/alternate within 3 days of reporting the event. Required documents that must be submitted include the following:

- SAE Form
- Concomitant Medication CRF pages
- AE CRF pages
- Copies of source documents pertinent to the event (lab reports, medical chart notes, etc.)
- Any other relevant information necessary to facilitate the investigator's judgment regarding the SAE's relatedness to the severity OR by request of the medical monitor/alternate

These documents must be submitted by either email attachments or via overnight courier.

7.2.2 Reporting to the IRB

Unanticipated problems involving risk to subjects or others, SAEs related to participation in the study and all subject deaths should be promptly reported by phone, email, or fax to the Brown University IRB.

An FDA cleared, CLIA waived urine drug test card will be used to assess candidates for recent use of opiates (i.e., morphine test), cocaine, amphetamines, methamphetamine, tetrahydrocannabinol (THC), buprenorphine, methadone, benzodiazepines, oxycodone, barbiturates, and 3,4-methylenedioxymethamphetamine (MDMA – also known as ecstacy). During screening subjects must be negative for all substances except THC. If positive for these drugs at other times during the study, the subject will not be removed from the study but should be asked about medication use and possibly re-evaluate their medical history for substance abuse.

Statistical Methods

8.1 Feasibility and Acceptability Endpoints

8.1.1 Primary Feasibility Endpoint

The number and percentage of subjects who completed the 6-week active medication phase will determine feasibility (target $\geq 70\%$).

8.1.2 Primary Acceptability Endpoint

The Client Satisfaction Questionnaire (CSQ-8), which ranges in scores from 8 to 32 (higher scores indicate higher satisfaction), will determine acceptability. Treatment satisfaction will be considered acceptable if the number and percentage of subjects who rate their treatment experience in the "satisfactory" or "highly satisfactory" range on the CSQ-8 is \geq 80%.

8.2 Secondary Outcome: Alcohol Craving Assessed in the H-LAB Paradigm

The secondary endpoint will be alcohol craving assessed during a laboratory alcohol-cue exposure paradigm, at study week 5. During the paradigm, participants rated their alcohol craving immediately following exposure to water cues and again immediately following exposure to alcohol cues. The primary outcome measure will be is the number and percentage of participants who report any level of alcohol craving during a laboratory alcohol-cue exposure paradigm (following exposure to alcohol cues) using the following single item: *How strong is your craving to drink alcohol?* Scores range from 0 (None) to 20 (Extremely Strong). Individuals who endorse any level of alcohol craving (e.g., > 1) are considered to

experience craving. Individuals who do not report any alcohol craving (e.g., 0) will be regarded as non-craving. Using generalized estimating equations, we compared the likelihood of alcohol craving as a function of medication condition.

Quality Control and Quality Assurance

This study will be conducted under International Conference on Harmonization (ICH) Good Clinical Practice (GCP) guidelines and all applicable regulatory requirements.

Actions to ensure the accuracy and reliability of data include the selection of qualified investigators and appropriate study centers; the review of protocol procedures with the investigator and study personnel prior to study start; the design of suitable source documents with appropriate instructions for use; the internal audit of source data according to GCP and internal procedures to ensure their accuracy, completeness, and verifiability; as well as the periodic site monitoring by the Sponsor's representatives (clinical monitors). The Project Coordinator or Project Director will review source documents and CRFs for accuracy and completeness. Any discrepancies will be resolved with the investigator, as appropriate.

Audits and Inspections

Authorized representatives of the Sponsor and the IRB may visit the site to perform audits or inspections, including source data verification. The purpose of the audit or inspection is to systematically and independently examine all study related activities and documents to determine whether these activities were conducted, and data were recorded, analyzed, and accurately reported according to the protocol, GCP guidelines, and any applicable regulatory requirements.

The principal investigator will notify the Brown University IRB and the sponsor, NIAAA, if contacted by a regulatory agency about an inspection.

Ethics

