The second primary objective is to leverage a human laboratory paradigm (H-LAB) to evaluate the effects of atomoxetine on an intermediate phenotype (alcohol craving) associated with alcohol use and outcomes in clinical trials. We hypothesize that atomoxetine, as compared to placebo, will decrease the likelihood of craving in the human laboratory during *in vivo* alcohol cue reactivity.

Methodology

This proof-of-concept study is a double-blind, randomized, placebo-controlled, parallel group, single-site clinical trial. After obtaining consent/parent permission/assent, potential subjects and, if younger than 18 years, their parent(s) will complete a medical history and psychiatric diagnosis interview (about the adolescent) to screen for eligibility. Youth will also complete a physical examination, vital signs, drinking history by the timeline follow-back (TLFB) method, alcohol breathalyzer test, Clinical Institute Withdrawal Assessment for Alcohol-revised (CIWA-AR), prior/current medication use, urine toxicology screen, clinical chemistry, and the Columbia Suicide Severity Rating Scale (CSSR-S). Females of child-bearing potential will have a pregnancy test.

If eligible for the study, 50 subjects will be randomized in an approximate 1:1 ratio (targeting 21 subjects per group – 42 subjects total) to either atomoxetine or placebo for 6 weeks.

Atomoxetine will be dosed at 40 mg/day for three days then increased to the maintenance dose of 80 mg (active) taken orally once daily (QD) for an additional 5.5 weeks. Subjects randomized to the placebo condition will be given an equal number of visually matched capsules.

At the randomization/baseline visit and after 4 weeks of investigational product administration (i.e., Study Week 5), subjects will undergo a human laboratory paradigm (i.e., alcohol cue reactivity assessment).

Number of Subjects (Planned): 50 (targeting 21 subjects per group – 42 subjects total)

Main Inclusion/Exclusion Criteria: Subjects will be male and female adolescents, ages 14 to 20 years old, who meet DSM-5 criteria for alcohol use disorder. They must be seeking to reduce their alcohol use.

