1.2 Human Laboratory Studies

Human laboratory studies of acute responses to alcohol, alcohol cues, or other experimental manipulations have progressed in important ways and hold potential to advance our understanding of how medications exert beneficial effects on drinking outcomes (18). These studies may help identify important individual difference factors affecting alcohol response, such as personality traits, drinking characteristics, and genotype, and aid in our understanding of the variability in cue and craving states, and provide additional information relevant to the design of clinical studies to assess the effectiveness of pharmacological agents.

The study to be conducted in this protocol utilizes an alcohol cue reactivity paradigm to attempt to recreate in the human laboratory risk conditions for relapse like those experienced by individuals with AUD in their natural environment. Alcohol cue reactivity, which involves systematic exposure to *in vivo* alcohol cues and simulates high-risk situations for relapse, is one of the most widely studied laboratory paradigms in the context of AUD (19, 20). Exposure to alcohol cues reliably elicits responses presumed to relate to the motivational processes that underlie drinking (21), and it is sensitive to medication effects among treatment seeking and non-treatment seeking adults and adolescents.

Impact on individual variability. Reactivity to alcohol and other drug cues varies from person to person, with some individuals showing little or no increase in target variables (e.g., craving) from the baseline or neutral cue trials to alcohol/drug cue trials (22-25). Some researchers have operationalized "responders" as individuals who show any change (22, 23, 26-28), whereas others have specified an exact minimum change (e.g., > 1-point increase in average craving) (25, 29, 30). Potential sources of variability include sex (31), genetic factors (32, 33), personality (26, 34), and substance use factors, such as lifetime alcohol

use indices and parental drinking problems (35), and these individual differences may moderate the effects of medications on alcohol cue reactivity (36-38).

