2.1 Primary Objectives

- Evaluate the feasibility, acceptability, and tolerability of atomoxetine (40 mg/day for 3 days then 80 mg/day thereafter) plus MET-CBT (i.e., "Path 180") for 6 weeks among adolescents with AUD as confirmed by the Diagnostic and Statistical Manual of Mental Disorders Fifth Edition (DSM-5TM).
- Apply our H-LAB paradigm to evaluate the effects of atomoxetine on intermediate phenotypes associated with alcohol use and outcomes in clinical trials. We hypothesize that atomoxetine, as compared to placebo, will reduce the likelihood of craving in the human laboratory during *in vivo* alcohol cue reactivity.

Study Interventions

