The H-LAB paradigm will follow our standardized procedures. Audio-recorded instructions ensure standardization within and across subjects. After attaching the physiological monitor (i.e., blood pressure cuff), the session begins with a 3-minute relaxation period that involves subjects sitting quietly and doing nothing. Then a 3-minute water trial begins, in which subjects hold and smell a glass of water as a standard procedure to control for the effects of simple exposure to any potable liquid, including all aspects of stimuli and movement except the nature of the beverage. A second 3-minute relaxation period follows the water trial. Next, subjects hold and smell a glass of their most desired or commonly consumed alcoholic beverage for two consecutive 3-minute alcohol trials. Order of water and alcohol trials is not counterbalanced due to known carryover effects. The water is accompanied by a commercially labeled water bottle and alcohol by the bottle or can from which it was poured and prepared as the teen usually drinks it. Across water and alcohol trials, subjects sniff the beverage for 5 seconds each time a tone sounds: 13 tones sound at variable intervals during each 3-minute block to ensure that all youth receive the same olfactory exposure. Observation via one way window ensures compliance. Subjects rate their alcohol craving after each 3-minute trial.

After every 3 minutes of exposure, each subject will rate his/her urge to drink alcohol using a visual analogue scale (VAS). The primary efficacy endpoint in the H-LAB is the "strength" of alcohol craving measured on a visual analogue scale (VAS; Item 1 below).

Following the H-LAB paradigm, subjects will receive a 7-day supply of the blinded study medication, and the dosing schedule will be reviewed. The subject will be instructed to bring the blister cards with them to the next visit so the project staff can perform drug accountability (capsule counts). The subject will also be instructed to contact project staff if they are experiencing any intolerable adverse events.

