6.2 Secondary Outcome: Alcohol Craving Assessed in the H-LAB Paradigm

The secondary endpoint will be alcohol craving assessed during a laboratory alcohol-cue exposure paradigm, at week 5. During the paradigm, participants rated their alcohol craving immediately following exposure to water cues and again immediately following exposure to alcohol cues.

The primary measure of alcohol craving will be the number and percentage of participants who report any level of alcohol craving during a laboratory alcohol-cue exposure paradigm using the following single item: *How strong is your craving to drink alcohol?* Scores range from 0 (None) to 20 (Extremely Strong). Individuals who endorse any level of alcohol craving (e.g., > 1) are considered to experience craving. Individuals who do not report any alcohol craving (e.g., 0) will be regarded as non-craving.

Safety Monitoring Plan

Safety monitoring will be conducted throughout the study; therefore, safety concerns will be identified by continuous review of the data by the principal investigator, clinic staff, medical monitor, and study nurses and physicians.

The Brown University IRB, medical monitor, principal and sub-investigators, and study nurses and physicians will review any safety concerns throughout the trial. In addition, a DSMB will participate in this study.

Quality control is central to all aspects of the activities detailed in this proposal to ensure clinical data accuracy and integrity. Day-to-day oversight of data quality will be delegated to the principal investigator, [name] and/or his designee. With assistance from our core team, he will provide direction with the development of data collection forms, recruitment and tracking databases, data management tasks, and statistical analyses and interpretation. The principal investigator or his designee will oversee the production of standard labels/codebooks for all data collection activities. He or his designee will oversee the production of reports that will track indices of project success, which will be reviewed weekly or biweekly at meetings of our core team, where issues or concerns will be deliberated and corrective action plans put into place.

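### The Week 5 endpoint counts any craving after alcohol cues and gives the same-session water rating no stated role, so alone it cannot support a claim about cue reactivity

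*Combined protocol and SAP*

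**What the plan says.** The hypothesis in section 2.1 is that atomoxetine, compared with placebo, "will reduce the likelihood of craving in the human laboratory during" in vivo alcohol cue reactivity; the synopsis says the same.

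Section 1.2, on variation between individuals, describes people who react weakly to cues as "showing little or no increase in target variables (e.g., craving) from the baseline or neutral cue trials to alcohol/drug cue trials".

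Section 4.7 sets out the session: a relaxation period, one water trial, a second relaxation period, then "two consecutive 3-minute alcohol trials". The water trial is there "as a standard procedure to control for the effects of simple exposure to any potable liquid". Craving is rated after each trial, so every completed session yields one water rating and two alcohol ratings.

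Sections 6.2 and 8.2 both say that craving is rated after water and again after alcohol. Section 6.2 then counts participants who "report any level of alcohol craving during a laboratory alcohol-cue exposure paradigm using the following single item". Section 8.2 counts the "number and percentage of participants who report any level of alcohol craving during a laboratory alcohol-cue exposure paradigm (following exposure to alcohol cues". Neither subtracts, compares with or adjusts for the water rating. Section 8.2 names generalized estimating equations (GEE) with medication condition as the only stated predictor. It does not say what the repeated observations are.

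**The concern.** The study runs a control trial in each session and collects the rating needed to use it, but the stated outcome and model do not use it. A subject who rates 8 after water and 8 after alcohol shows no reaction to the cue, yet counts the same as one who goes from 0 to 8.

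Two misreadings become possible. A drug that blocks the reaction to the cue can look weak or inactive, because subjects who already crave at the water trial still count as craving. A drug that only lowers background craving can be reported as reducing cue reactivity. The planned result cannot tell these apart.

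A smaller matter is that 6.2 does not say which trial counts, while 8.2 limits the count to ratings after the alcohol cues. Read literally, a subject who craves after water and rates 0 after both alcohol trials is a craver under 6.2 and not under 8.2.

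**Working it through.** The documents state no significance level, power, effect size or craving rate for this endpoint, so there is no planned figure to reproduce. The check is a bound that follows from the definition, then two illustrations on assumed rates.

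**1. Bound.** Let a be the share of placebo subjects who crave after alcohol and w the share who already crave after water, all of the latter also craving after alcohol. If the drug removes the whole cue-elicited increase and nothing else, the alcohol rating falls back to the water rating and the share craving after alcohol becomes w. The endpoint therefore falls by at most a − w. This holds for any cut-off for craving, provided the same one is applied to both trials.

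Neither share is in the documents. Assuming a = 90%:
- w = 30%: 90 − 30 = 60 points
- w = 50%: 90 − 50 = 40 points
- w = 70%: 90 − 70 = 20 points

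**2. Dilution of a true effect on the cue response.** Let t be the share already craving at the water trial and c the probability that the cue raises craving, taken as independent of t. Then P(any craving after alcohol) = t + (1 − t)c. Assume that the drug lowers c from 60% to 30% and leaves t unchanged.

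Power uses n = 21 per arm (the completer target in section 1.4) and an assumed two-sided 5% level: power = Φ{(d − 1.96√[2p̄(1 − p̄)/n]) / √[(p₁(1 − p₁) + p₂(1 − p₂))/n]}, where d = p₁ − p₂ and p̄ is the mean of p₁ and p₂.

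| t | Placebo, any craving | Drug, any craving | Difference | Power |
|---|---|---|---|---|
| 0 | 60% | 30% | 30 points | 50% |
| 20% | 0.2 + 0.8 × 0.6 = 68% | 0.2 + 0.8 × 0.3 = 44% | 24 points | 34% |
| 40% | 0.4 + 0.6 × 0.6 = 76% | 0.4 + 0.6 × 0.3 = 58% | 18 points | 23% |
| 60% | 0.6 + 0.4 × 0.6 = 84% | 0.6 + 0.4 × 0.3 = 72% | 12 points | 15% |

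A yes/no outcome of any rise from water to alcohol would stay at 60% against 30% (power about 50%) in every row. Both outcomes are binary, so the loss down the table comes from background craving and not from a change of scale. These figures are not the power of the continuous analysis proposed below; the documents give no standard deviation from which to compute that.

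**3. The reverse case.** Assume that the drug lowers only background craving, t from 60% to 30%, with c = 50% in both arms. Any craving is then 0.6 + 0.4 × 0.5 = 80% on placebo and 0.3 + 0.7 × 0.5 = 65% on drug. That is a 15-point difference with the cue response at 50% in both arms.

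**The case against.** The strongest reply is that the endpoint matches the hypothesis as written. The objective speaks of the likelihood of craving during alcohol cue reactivity, and 8.2 measures the likelihood of craving after alcohol cues. It does not promise an effect on an alcohol-minus-water increase. The wording in 1.2 comes from a literature summary, which notes that researchers define responders in different ways and adopts no definition for this trial. This stands, and it is why the binary endpoint can stay. It does not license a statement about cue reactivity if that endpoint is the only evidence.

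Four stronger readings are tempting, and the documents do not support them.

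- A reader might infer that the between-arm comparison is biased. It is not: randomisation makes background craving comparable between arms in expectation, and the comparison of post-cue craving is valid. The problem is specificity and dilution.
- A reader might infer that the endpoint counts craving at any point in the session. Section 8.2 is limited to ratings after alcohol cues.
- A reader might infer that 6.2 and 8.2 contradict each other. Section 6.2 is silent on the trial and 8.2 specifies it, so this is a wording gap. The pattern that separates them is probably uncommon, and the documents give no frequency for it.
- A reader might infer that the model excludes the water rating. GEE implies repeated observations, and a cue-type term is unspecified, not ruled out.

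It is also fair to say that some insensitivity of an any-craving outcome comes from reducing a 0–20 rating to yes or no. That loss would occur with or without a water control and is no part of this point.

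**Conclusion.** The point holds in a limited form. Section 8.2 measures any craving after alcohol cues, whether or not the cue raised it, and the control rating has no stated role. The result will support a statement about craving after cues. It will not on its own support a statement about cue reactivity.

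The firm part is textual, together with the bound a − w, which needs only the definition and the condition that those craving at water also crave after alcohol. The size in this trial is unknown because the documents give neither share. The ceilings of 60, 40 and 20 points, the power figures and the 80% against 65% case are illustrations on assumed rates. With little craving at the water trial, the loss would be small.

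This concerns a supportive analysis of an outcome that sections 6.2 and 8.2 call secondary, in a proof-of-concept trial. It is a cheap improvement and does not invalidate the planned comparison.

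**What to change.** - **Section 8.2, analysis.** Keep the binary endpoint. Add one pre-specified supportive analysis comparing arms on the Week 5 alcohol-trial rating on the 0–20 item, taken as the mean of the two alcohol trials, either minus the same-session water rating or adjusted for it as a covariate. Name one of the two forms in advance. A medication-by-cue-type term in the binary GEE is not a substitute: it estimates a ratio of odds ratios, not a mean difference on the rating, and the two can disagree.
- **Section 8.2, reporting.** State that a fall in any craving without a fall in the alcohol-versus-water contrast will be reported as lower craving after cues, not as reduced cue reactivity.
- **Section 6.2.** Insert the same restriction to ratings after the alcohol cues that 8.2 carries.

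The cost is plan wording and one extra model on ratings already collected, with no added procedure or burden on subjects. The downside is a second craving result that may disagree with the first; if the difference form is chosen, it also carries the noise of two ratings.
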